3.0 STUDY DESIGN OVERVIEW & RATIONALE

We will utilize a prospective Simon two-stage Phase II study design. Breast cancer patients who have completed primary active therapy for breast cancer (e.g. surgery, chemotherapy and/or radiation) and are currently taking maintenance aromatase inhibitors (AIs) such as anastrozole, letrozole or exemestane will be approached. We will assess response to the VRP with a blinded standardized interpretation of superficial vaginal epithelial cells. Entrance criteria will stipulate baseline measurements must be < 2%. If the subject has $\geq 4\%$ superficial vaginal cells on cytologic evaluation after the intervention period, then the response will be considered positive.

After documentation of eligibility according to the inclusion and exclusion criteria (**see Section 5.0**) and after enrollment, the subject will receive instruction in the VRP (**see Section 6.0** for details and **Study Schema**). Baseline demographic data, baseline vaginal cell cytology, vaginal pH, and PROs will be collected prior to initiating the VRP instruction. During the time on study, subjects will log their adherence to the prescribed therapy schedule of the VRP and AI therapy. Subjects will receive reminder contacts from study staff/team member 1 week and 1 month after initial instruction. These calls will function to ensure that subjects have had adequate instruction, and problem-shoot any issues with adherence to the program and logging adherence. The subject will return the journal at the 12-week study completion visit when vaginal cell cytology, vaginal pH, and PROs will be assessed.

The primary endpoint of percent superficial vaginal cells will be determined via blinded review by a board-certified pathologist experienced with interpretation of cytology. Secondary endpoints of pH will be logged at the time of the exams and PROs will be determined by standardized, validated scoring metrics for the respective PRO measures used. The exploratory analysis of AI adherence will be determined using patient-reported logs.

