5.0 SUBJECT ELIGIBILITY

5.1. Inclusion Criteria

Each potential subject must satisfy all of the following criteria to be enrolled in the study:

_____ **5.1.1** Females \geq age 18 diagnosed with Stage 0-3 breast cancer

_____ **5.1.2** Have completed active primary treatment

- Defined as surgery, chemotherapy and/or radiation for the treatment of breast cancer
- Does not include immunotherapy or other targeted therapies such as trastuzumab, CDK 4/6 or mTOR inhibitors

_____ **5.1.3** Have been receiving AIs for at least 6 months prior to enrollment

_____ **5.1.4** Plan to continue AIs for an additional 3 months

_____ **5.1.5** Amenorrhea for at least 12 months at enrollment regardless of cause

_____ **5.1.6** Participants must be able to read and write in English

_____ **5.1.7** Participants must have < 2% superficial vaginal cells on cytologic evaluation

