9.1.1 Pre-intervention cytology collections

A clinician trained in the collection of lower female genital tract cytology specimens will collect the vaginal cell cytology. The collection is done in a process similar to a routine PAP test. A swab is placed into the vagina and is wiped against the vaginal wall to collect cells and fluids. The amount collected will be equivalent to a routine PAP test. The cytology specimen will be transported to the pathology department inside a Biohazard bag inside an opaque sealed envelope. The specimen will be prepared by standard cytology techniques. Slides will be housed in a UWCCC research office.

At the end of the study, slides will be randomly labeled and organized such that it is impossible to identify timing of collection, or even if the slides are associated with the same participant. Following this blinding, all slides will be interpreted by a trained cytopathologist and destroyed after final study analysis.

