9.2.1 Post-intervention cytology collections

A clinician trained in the collection of lower female genital tract cytology specimens will collect the cytology. The amount collected will be equivalent to a routine PAP test. The cytology specimen will be transported to the pathology department and stored as documented in **Section 9.1.1**. At the completion of each stage of the study, all pre-intervention cytology collections and post-intervention cytology collections will be pooled and interpreted with the specimens blinded as to the timing of the collections.

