10.0 MEASUREMENT OF INTERVENTION EFFECT

10.1 Response

A positive response to the VRP intervention will be confirmed if the percentage of superficial vaginal cells changes from $< 2\%$ to $\geq 4\%$ from pre-intervention to post-intervention.

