Appendix 1 – Schedule of Events

	Enrollment^a	VRP instruction visit	1 Week Post-Instruction	1 Month Post-Instruction	12-week follow-up visit^d
Informed consent	X				
Eligibility checklist	X				
Baseline demographics		X			
PRO evaluations ^b		X			X
Cytology swab	X				X
pH collection	X				X
VRP Instruction		X			
Collect VRP use logbook					X
Phone Call ^c			X	X	

- A. The enrollment and VRP instruction visit may be conducted at the same time.
- B. The PROs will be: Vaginal Symptoms Questionnaire, NIH PROMIS Global Health scale, NIH PROMIS Female Sexual Function Profile, NIH PROMIS Global Satisfaction with Sex Life scale, NIH PROMIS Anxiety 8a scale, NIH PROMIS Depression 8a scale
- C. Phone calls to assess adherence
- D. +/- 4 weeks

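### If the <2% entry rule is enforced before slides are pooled, the percentage being scored hints at timing, so relabelling alone only partly masks a reader who knows the cut-offs

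*Combined protocol and SAP*

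**What the plan says.** **Entry.** Inclusion criterion 5.1.7 reads "Participants must have < 2% superficial vaginal cells on cytologic evaluation", and Section 3.0 repeats that "Entrance criteria will stipulate baseline measurements must be < 2" percent. Appendix 1 puts the baseline swab at enrollment and adds that "The enrollment and VRP instruction visit may be conducted at the same time".

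**Response.** Section 10.1: "A positive response to the VRP intervention will be confirmed if the percentage of superficial vaginal cells changes from" under 2% to at least 4%. Section 11.3 states only the post-intervention threshold of 4%.

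**Masking.** Section 9.1.1 has slides held in a research office until the end of the study, when "slides will be randomly labeled and organized such that it is impossible to identify timing of collection"; pairing is hidden as well. It continues: "Following this blinding, all slides will be interpreted by a trained cytopathologist and destroyed after final study analysis". Section 9.2.1 gives a different time: "At the completion of each stage of the study, all pre-intervention cytology collections and post-intervention cytology collections will be pooled and interpreted".

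**Decision rule.** Section 11.2 tests a 10% response rate against 30%. The trial stops if 1 or fewer of the first 15 women respond, and rejects the null if 6 or more of 25 respond.

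**Not stated.** The plan does not say who reads the baseline slide for 5.1.7, when, or from which slide. It does not say whether the endpoint reader knows the two cut-offs, how many cells are counted, or which baseline read counts if there are two.

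**The concern.** Blinded cytology is the main protection against reader bias in a single-arm trial whose endpoint is a judged percentage. Random labels hide timing only as far as the slide's content says nothing about timing. Here the variable used to select women at baseline is the same variable the blinded reader scores. If selection comes first, the baseline half of the pool is cut off at 2% and the other half is not.

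A reader who knows this, and who sees superficial cells, has some reason to think the slide was taken after the intervention and that a call of 4% or more creates a responder. The claim in 9.1.1 that timing cannot be identified is then too strong. Six responders decide the trial, so a small upward drift in calls could matter.

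**Working it through.** **1. The plan's own figure.** With p the response probability, 11.2 gives

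P(reject) = Σ (x = 2 to 15) Bin(x; 15, p) × P[Bin(10, p) ≥ 6 − x].

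At p = 0.10 the terms for x = 2, 3, 4, 5 and for x ≥ 6 are about 0.0034, 0.0090, 0.0113, 0.0068 and 0.0022, and the unrounded sum is 0.0328. At p = 0.30 the result is 0.8017. The stated 5% limit and roughly 80% power are reproduced.

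**2. How much a slide's content reveals.** With equal numbers of baseline and post-intervention slides, let b be the chance that a baseline slide reads at or above 2% in the blinded reading, and q the same chance for a post-intervention slide. Then

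P(post | reads ≥2%) = q / (q + b).

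With q = 0.30 (assumed):
- b = 0: 1.00
- b = 0.01: 0.30/0.31 = 0.97
- b = 0.05: 0.30/0.35 = 0.86
- b = 0.10: 0.30/0.40 = 0.75
- b = 0.20: 0.30/0.50 = 0.60

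The clue is strong only if screened baselines rarely read above 2% again.

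**3. Scenarios with counting variation.** The documents give no cell count, reader error or baseline distribution, so these inputs are assumed: 100 or 300 cells counted; mean true baseline 0.5%, 1% or 2% before screening; baselines screened at <2% on one count and then counted again; 30% of women moved to a true value between 4% and 12%, the rest unchanged. The 2% to <4% column is obtained by subtraction, (q₂ − q₄) / [(q₂ − q₄) + (b₂ − b₄)], where the subscripts denote reading ≥2% and ≥4%.

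| Mean baseline, cells | P(post given ≥2%) | P(post given ≥4%) | P(post given 2% to <4%) |
|---|---|---|---|
| 0.5%, 100 | 0.85 | 0.97 | 0.062/(0.062+0.054) = 0.53 |
| 0.5%, 300 | 0.91 | 0.996 | 0.036/(0.036+0.029) = 0.55 |
| 1%, 100 | 0.75 | 0.93 | 0.100/(0.100+0.109) = 0.48 |
| 1%, 300 | 0.84 | 0.99 | 0.061/(0.061+0.064) = 0.49 |
| 2%, 100 | 0.65 | 0.85 | 0.171/(0.171+0.208) = 0.45 |
| 2%, 300 | 0.73 | 0.97 | 0.116/(0.116+0.143) = 0.45 |

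Clearly high slides are recognisable. In these scenarios slides between 2% and 4% are close to a coin toss. They would reveal more if some women truly moved into that band, or if the second reading of a slide differed little from the first. With no effect at all, the ≥2% figure is about 0.50.

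**4. What a drift in calls would do to the test.** Suppose 20% of women have a true post value of 2% to <4%, and 10% to 20% of those are read up to ≥4% (both assumed). The apparent null rate becomes:
- 0.10 + 0.20 × 0.10 = 0.12, giving P(reject) = 0.070
- 0.10 + 0.20 × 0.20 = 0.14, giving P(reject) = 0.125

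If every trial that continued and ended with exactly five responders gained one more, the effective final cut-off would be 5 of 25 and P(reject) would be 0.093.

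Downward misreads offset this. With 10% of the band read up and 10% of responders read down, the rate is 0.02 + 0.10 × 0.90 = 0.11 and P(reject) = 0.049. With 20% read down it is 0.02 + 0.10 × 0.80 = 0.10, which returns 0.033.

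**The case against.** The strongest objection is that the premise is not established. Neither 9.1.1 nor 9.2.1 describes any reading before the pooled one. If the blinded reading is the only one, the pool may hold baselines at or above 2% (8% to 47% of them under the assumptions in step 3), and the clue largely goes. This stands as a limit on the point, which is conditional on screening before pooling. It does not remove it: 5.1.7 is a condition of enrollment and 9.1 speaks of eligibility being verified, so the plan as written implies an earlier read that it does not describe. If there is none, 5.1.7 cannot be applied at entry, and the same sections still need amending.

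Second, labels and pairing stay hidden, and the only clue is the quantity being scored. Bias needs a reader who knows the cut-offs, reasons back to timing and shifts calls. Sections 3.0 and 11.2 call for a blinded, standardized interpretation by a board-certified pathologist, and silence about the cut-offs is not evidence that they are known. This also stands.

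Third, a reader might infer that any slide at or above 2% is almost certainly post-intervention, that masking fails, or that borderline slides are the most exposed. The documents do not support these readings. Near-certainty needs almost no baseline to read above 2% again, and in the scenarios the borderline band is the least identifiable part of the upper range.

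**Conclusion.** The point holds in a limited form. If the entry rule is enforced before pooling and the intervention has an effect, a slide with many superficial cells is more likely to be post-intervention, and relabelling cannot make timing unidentifiable. Because the plan does not keep the cut-offs from the reader, upward shifts in borderline calls are possible and no control group would show them.

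Masking is weakened, not lost. The size of any bias cannot be derived from the documents. The rise from 3.3% to between 7.0% and 12.5% illustrates sensitivity to one-way misreading at assumed rates; it is not an estimate, and balanced misreading would remove most or all of it. The amendment is worth making because it costs little and helps under either reading schedule. The undescribed eligibility read and the conflict between 9.1.1 and 9.2.1 need settling in any case: the stage 1 stopping rule in 11.2 needs responses from the first 15 women, which a reading made only at the end of the study would not supply.

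**What to change.** Amend 9.1.1 and 9.2.1 as follows.

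1. The endpoint reader is not told the <2% and ≥4% cut-offs and records, for each slide, only the number of superficial cells and the total cells counted. The statistician computes the percentage and applies the cut-offs after unblinding.
2. State who reads the baseline slide for 5.1.7, when, and which baseline read defines response. Where existing staff allow, this person is not the blinded endpoint reader.
3. Reconcile 9.1.1 (end of study) with 9.2.1 (end of each stage).
4. Optional: if an eligibility read is done and consent allows, keep the slides of women who failed 5.1.7 and add them, relabelled, to the pool, so that a slide with superficial cells is not by construction post-intervention. This works only if those slides exist and are retained.

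Items 1 to 3 are protocol wording plus a recording form, with no extra swab or visit. Item 2 may call for a second person at the eligibility read. Item 4 adds a few slides to read.

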9.1.2 Pre-intervention vaginal pH collections

At the time of cytology collection, standard clinical-grade pH paper will be used to swab the vagina to assess vaginal pH. This will be interpreted by a clinician blinded to the study and recorded by the clinician.

9.1.3 Pre-intervention PRO assessments

If the subject has been found eligible, gives written consent and is enrolled, baseline demographic data will be gathered from the patient and the medical record and baseline PROs will be collected. PROs being assessed in this study will be: Vaginal Symptoms Questionnaire, NIH PROMIS Global Health scale, NIH PROMIS Female Sexual Function Profile, NIH PROMIS Global Satisfaction with Sex Life scale, NIH PROMIS Anxiety 8a scale, NIH PROMIS Depression 8a scale. PROs will be completed at the instructional visit, prior to receiving the instructions.

All PRO assessments will be done electronically via REDCap, UW Qualtrics, or on paper at the UWCCC/UWHC..

They will require approximately 20 minutes to complete. If the surveys are completed on paper, a member of the study staff will collect the PRO assessments in an opaque-sealed envelope and transport them to the secure locked study office that is administering this study. Surveys will be identified by study ID and date of completion to protect confidentiality of subject.

9.2.1 Post-intervention cytology collections

A clinician trained in the collection of lower female genital tract cytology specimens will collect the cytology. The amount collected will be equivalent to a routine PAP test. The cytology specimen will be transported to the pathology department and stored as documented in **Section 9.1.1**. At the completion of each stage of the study, all pre-intervention cytology collections and post-intervention cytology collections will be pooled and interpreted with the specimens blinded as to the timing of the collections.

9.2.2 Post-intervention vaginal pH collections

At the time of cytology collection, standard clinical-grade pH paper will be used to swab the vagina to assess vaginal pH. This will be interpreted by a clinician blinded to the study and recorded by the clinician.

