5.2.8 Any use of the VRP off study within the last 6 months

6.0 DOSAGE AND ADMINISTRATION OF INTERVENTION

The VRP is a standardized program. The description has been put into pamphlet form and will be given to the subjects as part of the study materials.

For the external component, the program begins by instructing the subject to use a quarter-sized amount of moisturizing lubricant on the fingers. Using this moisturizer, a press-release motion is taught to be used over the entire vulva. This is repeated for the vaginal introitus. These activities are encouraged to be performed 3 to 4 days per week.

For the internal component, the instructor will select the appropriate size of the FDA-approved vibrating vaginal wand to be used in this study. The subject will be instructed in the proper lubrication of the vibrating wand and how to insert it to the deepest comfortable depth. When the vibration function is activated, the subject is instructed to find a comfortable position and allow a 5-minute vibration cycle. These activities are encouraged to be performed 3 to 4 days per week.

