7.2 Program materials

Subjects will receive personal lubricant in sufficient quantity to perform the program per protocol for 12 weeks. They will also receive the FeMani Vibrating Massage Wand free of charge. This a class 1 durable medical device approved by the FDA.

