9.4 Study Completion Visit

All subjects will be asked to return 12 weeks (+/- 4 weeks) after in-person instruction of the VRP program. Subjects will complete post-intervention PROs prior to undergoing vaginal swab/collection. Subjects will be asked to bring and turn in the logbooks for analysis.

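### Follow-up vaginal pH is read from a site that receives study lubricant 3 to 4 days a week, baseline pH is not, and no sampling condition separates residual product from physiological change

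*Combined protocol and SAP*

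**What the plan says.** Lubricant is part of the intervention. Section 6.0 describes an external component, "Using this moisturizer, a press-release motion is taught to be used over the entire vulva. This is repeated for the vaginal introitus", and an internal one: "The subject will be instructed in the proper lubrication of the vibrating wand and how to insert it to the deepest comfortable depth". The same frequency is given for each: "These activities are encouraged to be performed 3 to 4 days per week". Section 7.2 covers supply: "Subjects will receive personal lubricant in sufficient quantity to perform the program per protocol for 12 weeks". The product's composition and pH are not stated.

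Baseline sampling comes first. Section 3.0: "Baseline demographic data, baseline vaginal cell cytology, vaginal pH, and PROs will be collected prior to initiating the VRP instruction". Appendix 1 places both baseline swabs in the enrollment column and allows enrollment and instruction to share a visit. Follow-up sampling is at the completion visit (Section 9.4): "All subjects will be asked to return 12 weeks (+/- 4 weeks) after in-person instruction of the VRP program".

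The cytology swab is described in Section 9.1.1: "A swab is placed into the vagina and is wiped against the vaginal wall to collect cells and fluids". pH is taken on the same occasion, in identical words at baseline (9.1.2) and follow-up (9.2.2): "At the time of cytology collection, standard clinical-grade pH paper will be used to swab the vagina to assess vaginal pH". Section 4.1 sets a single arm. Section 2.3.1 makes within-subject pH change a secondary objective, and Section 11.4 plans to relate it to change in cytology and in patient-reported outcomes.

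**The concern.** With no control arm, any systematic difference in sampling conditions between the two visits is counted as effect. Here the plan builds one in: study lubricant reaches the sampled site between the two measurements, and the follow-up swab may be taken at any time after the last use.

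The introduction says little published evidence supports a change in vaginal physiology from the programme, and the hypothesis in Section 2.1 names pH. A reading that reflects product left on the vaginal wall would not answer that question, although lubricant is part of the programme.

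The correlations in Section 11.4 are exposed too. A frequent user is more likely to be sampled soon after use. If frequent users also differ in cytology or symptom change, residual product could create or mask an association with pH.

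**Working it through.** **The plan's own figures.** None is given for pH: no power, standard deviation or margin. The only design figures, in Section 11.2, concern cytology: 15 then 25 patients, stop at 1 or fewer responses, reject the null at 6 or more. They reproduce:

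P(reject | p) = sum over x from 2 to 15 of P(X1 = x; 15, p) × P(X2 ≥ 6 − x; 10, p)

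- At p = 0.30: 0.802, against a stated power of about 80%.
- At p = 0.10: 0.033, within the stated 5%.

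The sampling question leaves this design unchanged and gives no corrected sample size.

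**The two visits compared.**

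| | Baseline | Follow-up |
|---|---|---|
| Study lubricant before the swab | None, by timing (3.0, Appendix 1) | 3 to 4 days a week (6.0) |
| Subject's own lubricant or moisturizer | Not barred (5.2 bars estrogens only), not recorded | Not addressed |
| Condition on recent use before pH | None (9.1.2) | None (9.2.2) |
| Record of use | Not applicable | Logbook (7.3, 9.3), not linked to sampling |

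**Chance of recent exposure at follow-up.** Input: k = 3 or 4 days of wand use per week (6.0). Assumptions, not in the documents: use days fall at random within the week, and adherence is full up to the visit.

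- Use on the day before sampling = k/7: 3/7 = 0.429 and 4/7 = 0.571.
- Use on at least one of the two days before = 1 − C(5,k)/C(7,k): 1 − 10/35 = 0.714 and 1 − 5/35 = 0.857.

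Section 8.2 allows for subjects below 3 days a week. At an assumed k = 2 the chances are 2/7 = 0.286 and 1 − C(5,2)/C(7,2) = 1 − 10/21 = 0.524.

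The one- and two-day windows are illustrative, since the documents do not say how long residue lasts. The pH error cannot be computed from them.

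**Room in the schedule.** The programme leaves 7 − 4 = 3 to 7 − 3 = 4 free days a week, and the visit may fall from week 8 (12 − 4) to week 16 (12 + 4).

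**The case against.** Several objections stand in part.

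- **Use is logged.** Section 9.3 asks for the days on which the programme was performed, and logbooks are returned at the completion visit, so days since last use might be derived. Section 7.3, however, describes weekly counts, so day-level detail is uncertain. No section uses the log to time or qualify a sample.
- **The baseline contrast is not absolute.** It holds for study lubricant only; some women may use their own products before baseline. That makes baseline exposure unknown and is a reason to record it at both visits.
- **Lubricant belongs to the package.** A lasting effect of it is a legitimate part of the programme's effect. Only transient residue would be artefact, and the documents do not show that it occurs.
- **Some women may have stopped before the swab.** Supply covers 12 weeks and the visit may fall at week 16. That is unplanned variation, not a set interval.
- **The pamphlet is not among the documents** and could contain a preparation instruction.
- **Readers are blinded.** This protects interpretation of slide and paper, but cannot remove product already in the specimen.

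A reader might go further and infer that the primary endpoint is biased and its type I error inflated. The arithmetic is easy to produce. If an assumed 2%, 5% or 10% of true non-responders crossed the 4% threshold through artefact, the response rate under the null would be 0.10 + 0.90 × 0.02 = 0.118, 0.145 or 0.190, and the chance of rejection 6.5%, 14.2% or 33.1%. But those rates are invented. Nothing in the documents says that lubricant shifts the superficial-cell percentage, or in which direction.

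**Conclusion.** The concern holds for the secondary pH endpoint. Study lubricant reaches the sampled site after baseline, neither pH section sets a condition on recent use, and a single arm cannot separate residue from physiological change. The planned correlations with pH change share the weakness.

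Under full adherence and random use days, exposure is likely: 43-57% on the day before and 71-86% within two days. It would be wrong to read these as the share of biased readings or as the size of a pH shift; the documents support neither. For cytology, an effect is possible but not shown. The stopping and rejection rules use cytology alone, so the trial's formal decision is not shown to be affected. The point merits an amendment because a difference in sampling conditions is cheap to prevent and hard to repair once the samples are taken.

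**What to change.** - **Sections 9.2.1 and 9.2.2:** schedule the completion swab after an interval without vaginal lubricant or moisturizer. The investigators set the length, timed within the programme's free days and the existing visit window. If the pamphlet already holds such an instruction, bring it into Section 9.
- **Sections 9.1.1, 9.1.2, 9.2.1 and 9.2.2:** at each swab, record the product and the time of last use, including the subject's own products.
- **Baseline:** record and flag recent use rather than require abstention. Consent and swab may share a visit, so an abstention instruction could have to precede consent.
- **Section 11.4:** report pH change with and without samples taken inside the interval.

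The cost is one added visit notice, one data field, and some visits rescheduled or flagged. The notice is new: Section 8.1 schedules contacts only at 1-2 weeks and 1 month. Whether the interval fits without touching the programme depends on the length chosen.
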